## 2. PREVIOUS RESEARCH

Postpartum contraception is important because unintended pregnancy rates range from 10%-20% in the first year postpartum.(6, 7) Lactational amenorrhea (LAM) can be effective contraception for up to 6 months.(8) However, many US women stop breastfeeding soon after delivery. By two weeks postpartum, an estimated 59% of US women started supplementation (2) and 37% of women stopped breastfeeding.(9) If sexually active and not using contraception, such women are at risk for unintended pregnancy.

Postpartum visits in the US generally occur 4-6 weeks after delivery.(10) Although 85% of women return for postpartum visits,(11) approximately half of women initiate sexual activity before six weeks postpartum and 82% are sexually active by 12 weeks postpartum.(12) Since ovulation can occur by 4 weeks postpartum in non-breastfeeding women,(13) experts recommend that women who are not exclusively breastfeeding should initiate contraception by 3 weeks postpartum.(14) Some also recommend that the postpartum visit should occur by 2-4 weeks postpartum in order to address contraception, breastfeeding, and postpartum depression,(14, 15) since postpartum depression affects 10%-15% of mothers (16) and can be associated with poor maternal-infant interactions and attachment.(17) Studies of the association of depression and breastfeeding discontinuation are conflicting.(18-20) One study of norethisterone enanthate given within 48 hours of delivery found an increased risk of postpartum depression,(21) but no studies have examined the effect of timing of DMPA administration on postpartum depression, contraceptive use, or breastfeeding.

Breastfeeding has many benefits, including immunologic protection and nutrition for the infant, more rapid uterine involution, decreased postpartum bleeding, and improved infant-bonding.(22) Exclusive breastfeeding for at least six months is recommended by the American College of Obstetricians and Gynecologists and the World Health Organization.(22, 23) However, only 41% of children in the National Immunization Survey were breastfed for 6 months.(24)

Because progesterone withdrawal may be the stimulus that initiates lactogenesis II, administration of progestin-only methods shortly after delivery could possibly inhibit or alter lactation.(25) Theoretically, a delay in the onset of lactation could lead to early formula supplementation and reduced exclusivity of breastfeeding. Prior studies of progestin-only methods have not found detrimental effects on infant growth or development (26, 27) or adverse impact on breastfeeding.(1-3) Accordingly, the US Medical Eligibility Criteria for Contraceptive Use (MEC) considers DMPA administration <4 weeks postpartum to be category 2, meaning the advantages generally outweigh the risks.(28) However, none of the studies reviewed by the authors of the US MEC were randomized trials, and thus may be subject to residual confounding, since women who choose DMPA differ from women who choose non-hormonal contraception, so use of the latter group as a comparator is incorrect. Also, some studies did not investigate timing of DMPA initiation (1, 2) or long-term DMPA continuation rates.(2) Most importantly, we recently found a significant difference in breastfeeding continuation in a randomized trial comparing immediate postplacental LNG-IUD insertion to delayed insertion at 6-8 weeks after vaginal delivery. In our study, only 9% of women who initiated breastfeeding and received a postplacental LNG-IUD were breastfeeding at 6 months compared to 41% of women who received an IUD at 6-8 weeks ( $p=0.006$ ).(4)

Since serum progestin levels with the LNG-IUD are much lower than with DMPA and given the limitations of previous studies of DMPA use by breastfeeding women, it is vital that we rigorously evaluate the effects of timing of postpartum DMPA administration on breastfeeding continuation, use of effective contraception, and postpartum depression.

### **3. RATIONALE**

DMPA is frequently given prior to hospital discharge in the US due to concerns that women will not follow-up for postpartum contraception. Given the severe limitations of currently published literature on breastfeeding following DMPA administration, and the recent study suggesting that immediate postplacental LNG-IUD insertion could negatively impact breastfeeding continuation, a properly performed randomized study to evaluate the use of immediate or delayed postpartum DMPA administration is needed. This study will be valuable in helping clinicians provide accurate advice to patients about potential effects of early DMPA administration on breastfeeding continuation, contraceptive use, and postpartum depression.

#### **4. RELEVANCE TO SFP**

This study is a high-priority topic for SFP since it focuses on the effects of immediate postpartum use of progestin-only contraception on breastfeeding performance.

#### **5. RESEARCH DESIGN AND METHODS**

**5.1 Overview:** We will enroll 184 pregnant subjects who plan to breastfeed and use DMPA for postpartum contraception. Subjects will be randomized to IM DMPA administration prior to hospital discharge or at 4-6 weeks after delivery (in the office of their primary obstetrician or midwife). Follow-up phone calls will be conducted at 2, 4, 6, 8, 12, 16, 20, 24, and 28 weeks after delivery. We will assess duration of exclusive and total breastfeeding, contraceptive use at 3 and 6 months, and rates of postpartum depression.

##### **5.2 Criteria for selection of subjects**

Inclusion criteria:

- 1.) Age  $\geq$  18 years old at time of enrollment
- 2.) Gestational age of 24 0/7 weeks or higher, or postpartum, and have not already received DMPA
- 3.) Planning to deliver at Magee-Womens Hospital and to breastfeed
- 4.) Plans to use DMPA for postpartum contraception for at least 6 months, or plans to use DMPA for postpartum contraception until starting a more effective form of contraception such as an intrauterine device, contraceptive implant, or sterilization
- 5.) Willing and able to provide informed consent in English and to comply with study protocol

Exclusion criteria:

- 1.) Intolerance of irregular vaginal bleeding
- 2.) Severe coagulation disorder
- 3.) Severe liver disease (LFTs  $>2x$  upper limits of normal at time of randomization)
- 4.) Contraindications to breastfeeding: maternal HIV infection; active herpes simplex with breast lesions; active varicella; active, untreated tuberculosis; antineoplastic, thyrotoxic, or immunosuppressive medications; concern that the infant may have galactosemia
- 5.) History of breast cancer, reduction or augmentation surgery
- 6.) History of severe clinical depression
- 7.) Multiple gestation

**5.3 Subject recruitment:** Potential subjects will be identified during prenatal care by their primary obstetrician, midwife after receiving routine counseling for postpartum contraception, or on the

postpartum floor. If a woman is interested in the study, the primary obstetrician, postpartum nurse, or midwife will call the Center for Family Planning Research (CFPR). The potential subject will be scheduled for a visit in CFPR for screening and enrollment, or seen in-person on the postpartum unit.. Each subject will receive routine care from her primary obstetrician or midwife throughout her pregnancy, during delivery, and postpartum except as discussed per the research design.

**5.4 Screening and enrollment:** Pregnant women will be screened to ensure they meet all entry criteria.

Data collection on enrollment will include:

- a. Demographic information
- b. Medical history (including height and prepregnancy weight), obstetric and gynecologic history (including breastfeeding experience and contraceptive history)
- c. Psychiatric history (including depression, anxiety and substance use)
- d. Breastfeeding intentions as measured by the Infant Feeding Intentions Scale (29)
- e. Psychosocial factors that can affect breastfeeding discontinuation, such as family/friend support for breastfeeding, plans for return to work/school, and confidence in ability to breastfeed (18)

**5.5 Subject allocation:** An independent individual will prepare allocation packets using a computer generated random number table. These packets will be placed in a sequentially numbered opaque tamper-resistant sealed envelope. Equal numbers of subjects will be randomly allocated to the following groups:

- 1.) Group 1. DMPA administration prior to hospital discharge.
- 2.) Group 2. DMPA administration at 4-6 weeks after delivery.

**5.6 Admission for delivery:** Research staff will check the hospital census daily for any study subjects. Obstetricians and midwives will be asked to contact the investigators after a subject's delivery and prior to hospital discharge. For women who will enroll in the study postpartum, a member of the postpartum staff or the medical team taking care of the patient will notify the patient of the available study. If the patient is interested in discussing the study with a member of the study team, the postpartum staff member will contact the research office. The verbal permission will be documented by the referring staff member, and filed in the research chart. A member of the research team will proceed with obtaining informed consent, and complete the visit on the postpartum unit. Day of delivery will be considered Day 0. Prior to hospital discharge (and ideally on postpartum day 1), subjects will be interviewed by research staff to assess whether she has initiated breastfeeding and remains eligible for the study. If she has not attempted breastfeeding at least once, does not plan to breastfeed, and/or no longer plans on using DMPA postpartum for contraception, she will be excluded from the study. All other exclusion criteria will again be reviewed to ensure that the subject has not developed any contraindications to DMPA administration

or breastfeeding. If entry criteria are satisfied, the next lowest numbered randomization packet will be opened to determine randomization allocation. All subjects will be informed that pelvic rest is advised for 4-6 weeks.

- 1.) Group 1: An investigator will order DMPA to be administered prior to hospital discharge. The subject's subsequent DMPA injection will be due 11-13 weeks after the injection. The subject will follow up with her primary obstetrician or midwife for further DMPA administrations.
- 2.) Group 2: The subject will be asked to follow up with her primary obstetrician or midwife at 4-6 weeks after delivery for DMPA administration or to start a more effective form of contraception such as an IUD or implant, or to be scheduled for sterilization. She will be instructed to use condoms until her follow-up visit if she is not abstinent. She will also be instructed on emergency contraception use.

A questionnaire about breastfeeding intentions and whether lactogenesis II has occurred (i.e. the mother's "milk has come in") will be administered prior to discharge. Information about the delivery and postpartum course will be collected, including type of delivery, birth weight, gestational age, Apgar scores, and subject's height and weight at time of delivery. The subject's primary obstetrician or midwife will be notified of plans for administering the woman's next dose of DMPA. Routine postpartum care (including referrals for lactation consultation or behavioral health services) will be provided by the subject's primary obstetrician or midwife. Any subject who decides to use an alternate form of contraception after randomization will be followed per protocol. The 2-week follow-up phone contact will be scheduled prior to discharge.

**5.7 Follow-up contacts:** Subjects will be contacted by phone at the following time points:

1) Week 2: day 12-19 (goal day 14)	6) Week 16: day 108-118 (goal day 112)
2) Week 4: day 26-33 (goal day 28)	7) Week 20: day 136-146 (goal day 140)
3) Week 6: day 40-47 (goal day 42)	8) Week 24: day 164-174 (goal day 168)
4) Week 8: day 54-61 (goal day 56)	9) Week 28: day 192-202 (goal day 196)
5) Week 12: day 80-90 (goal day 84)	

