#### *OUTCOME ASSESSMENTS*

- A questionnaire about breastfeeding (including psychosocial factors related to breastfeeding and introduction of alternatives to breastmilk) and contraceptive use will be administered at each contact. Timing of lactogenesis II will be assessed at Week 2 unless it occurred prior to discharge. Timing of postpartum sexual activity initiation will also be assessed. At any point when the subject reports cessation of breastfeeding, a questionnaire will be administered to assess reasons for discontinuation.

- The Edinburgh Postnatal Depression Scale (EPDS) will be administered at each contact as a screening tool for postpartum depression.(5) If a subject scores  $\geq 12$  on the EDPS, she will be referred to the Magee Behavioral Health clinic or to a behavioral health clinic of her choice and her primary obstetrician or midwife will be notified.
- Subjects will be asked if they had any visits with their primary obstetrician, midwife, or any other provider since the last contact. Records will be requested from all reported visits.
- The next telephone contact will be scheduled (when applicable).

**5.8 Data analysis:** Analysis will be performed using Stata 10 (StataCorp LP, College Station, TX).

- 1) The primary analyses will use intention-to-treat data. The intention-to-treat group will be defined as all randomized subjects. Infants who are fed pumped breastmilk will be considered as breastfeeding. Exclusive breastfeeding will be defined as breastfeeding without introduction of alternatives to breastmilk. A secondary analysis looking only at women who received at least one injection of DMPA will also be performed.
- 2) Survival analysis will be used for all time series data, including time to discontinuation of breastfeeding and time to introduction of alternatives to breastmilk. Data will be censored at the last date of contact. Breastfeeding will be the outcome variable. The log-rank test will be used for unadjusted comparison of the groups and presented graphically using a Kaplan-Meier curve. Cox proportional hazards model will be used to control for age, race, education, marital status, and prior breastfeeding experience while examining the association between timing of DMPA administration and discontinuation of breastfeeding.

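### Gestational age at birth is recorded and fixed before randomization, but no eligibility rule, model covariate or separate analysis uses it, so preterm births that pass a partial filter can add noise to the breastfeeding outcomes.

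*Combined protocol and SAP*

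**What the plan says.** **Enrollment (section 5.2).** Inclusion criterion 2 reads "Gestational age of 24 0/7 weeks or higher, or postpartum, and have not already received DMPA". It fixes when a woman may enroll. The postpartum route carries no gestational-age limit. Among the exclusions, the pregnancy-type item is "Multiple gestation" and the only item about the infant is "concern that the infant may have galactosemia".

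**Re-screening (section 5.6).** After delivery, a woman is excluded under this condition: "If she has not attempted breastfeeding at least once, does not plan to breastfeed, and/or no longer plans on using DMPA postpartum for contraception". In addition, "All other exclusion criteria will again be reviewed to ensure that the subject has not developed any contraindications to DMPA administration" or to breastfeeding. Only then is she allocated: "If entry criteria are satisfied, the next lowest numbered randomization packet will be opened to determine randomization allocation".

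**Data collected (section 5.6).** The delivery record includes "type of delivery, birth weight, gestational age, Apgar scores".

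**Analysis (section 5.8).** Item 1 makes all randomized women the primary set, counts pumped milk as breastfeeding, and names one other analysis set, women who received at least one injection. Item 2 uses the log-rank test for the unadjusted comparison and a Cox model to "control for age, race, education, marital status, and prior breastfeeding experience". Gestational age, birth weight and Apgar scores do not appear anywhere in section 5.8.

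**The concern.** The breastfeeding outcomes are time to stopping and time to introducing alternatives to breastmilk. When an infant is very immature, either event may follow from the infant's condition, whichever arm the mother is in. Section 2 describes the mechanism under test: early progestin may disturb the onset of lactation and so lead to early supplementation. Supplementation that follows from prematurity is recorded as the same event.

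The re-screening step tests whether the mother has attempted and still intends to breastfeed, not whether the infant can feed. The plan also does not say whether pumping counts as an attempt. A woman who enrolled at 25 weeks and delivered at 27 could therefore be randomized if she had attempted once and still planned to breastfeed.

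Three things are at stake: precision, because a variable likely to predict the outcome is left out of a model that already adjusts for others; a diluted contrast, if timing matters less in these women; and an uneven split of a small number of preterm births, which the five listed covariates are not chosen to correct.

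**Working it through.** **1. Reproduce the design (section 5.9).** Inputs: 0.35 against 0.60 at 6 months, two-sided Fisher's exact test, significance level 0.05, 70 per group.
- Exact enumeration of the Fisher test gives power 0.809, in line with the stated 80%.
- Inflation: 140 / (0.90 × 0.85) = 183.01, which rounds up to the stated 184.

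The plan's own figures stand.

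**2. Dilution if timing has no effect in preterm births.** The documents give no preterm share, so let d be an assumed share of randomized women and c their common 6-month rate in both arms.
- Group 1 rate: (1 − d) × 0.35 + d × c
- Group 2 rate: (1 − d) × 0.60 + d × c
- Difference: (1 − d) × 25 points

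For example, with d = 0.05 and c = 0.20, the rates are 0.95 × 0.35 + 0.05 × 0.20 = 0.3425 and 0.95 × 0.60 + 0.05 × 0.20 = 0.58.

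| Assumed share d | Difference (points) | Fisher power, 70 per arm |
|---|---|---|
| 0 | 25 | 0.809 |
| 1% | 24.75 | 0.801 |
| 2% | 24.5 | 0.792 |
| 5% | 23.75 | 0.765 |
| 10% | 22.5 | 0.717 |

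The table uses c = 0.20. Moving c to 0.35 or 0.60 changes power by less than 0.005.

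**3. The same check if some effect remains.**
- Half the effect kept (0.20 against 0.325 in preterm births): power is 0.788 at d = 5% and 0.766 at d = 10%.
- Full 25-point effect at lower rates (0.15 against 0.40): power stays at 0.81 at both shares.

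Lower breastfeeding rates alone therefore cost no power. The loss in step 2 comes wholly from the assumed absence of effect.

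**4. Chance imbalance.** Section 5.5 states equal allocation and no stratification. Suppose 14 of 140 women (10%, an assumption) have preterm births, with 70 women per arm. By the hypergeometric distribution, a split of 9–5 or more uneven in either direction has probability 0.40, and 10–4 or more uneven has probability 0.16.

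**5. Is the variable safe to adjust for?** Section 5.6 places delivery before the packet is opened, so gestational age at birth cannot be affected by allocation. Adjusting for it, or restricting a supportive analysis by it, does not break the randomized comparison.

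**The case against.** The strongest case on the other side has five parts.

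- **There is a filter.** A reader might infer that very preterm births enter unrestricted and that the infant's ability to feed plays no part. The documents do not support that. Section 5.6 requires an attempt and a continuing plan, and contraindications are reviewed again. Section 5.11 allows 10% for exclusions before randomization. This stands: the filter is real, though indirect and incomplete.
- **The 24-week criterion is not the cause.** It limits enrollment, not birth, and postpartum enrollment would leave the same route open if it were raised. This also stands.
- **There is no bias.** A reader might infer confounding. Randomization follows delivery, so preterm birth is balanced in expectation. Section 5.11 also says that the intention-to-treat analysis is meant to carry over to real-life situations, which argues against excluding these women. This stands.
- **The size is speculative.** No preterm share is documented, and neither is an absence of effect in that group. The proposed mechanism is maternal and is not confined to term births. Nor do the documents say that 0.35 and 0.60 are rates for term births only, so the planning rates may already include preterm births. This stands, and it makes the power figures an illustration rather than a correction to section 5.9.
- **The remedy does not match the illustrated loss.** A Cox covariate leaves the log-rank and proportion tests as they are, and gestational age does not identify ill term infants. This stands as a limit on what the fix achieves.

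None of this explains why a baseline variable that is already collected should stay out of an adjusted model that the plan already intends to fit.

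**Conclusion.** The point holds as a minor improvement in pre-specification. Gestational age at birth is recorded and fixed before randomization, yet the plan does not use it for eligibility, adjustment or any separate analysis, and re-screening removes only some of the affected women. The consequences are lost precision, possible dilution and chance imbalance, not systematic bias.

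The size is uncertain. If the preterm share is 1% to 2%, the loss of power is negligible even with no effect of timing in that group. It becomes noticeable, at 0.77 to 0.72, only if the share is 5% to 10% and timing has no effect there. It shrinks if part of the effect remains and disappears if the full difference remains. The share and the absence of effect are both assumptions. The figures do not show that the trial is underpowered.

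**What to change.** In section 5.8 item 2:

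1. Add gestational age at delivery to the Cox covariates. State that the adjusted model applies both to breastfeeding discontinuation and to introduction of alternatives to breastmilk, since the current sentence names only the first.
2. Pre-specify a supportive sensitivity analysis of the breastfeeding outcomes in term births (37 weeks or later). Keep the intention-to-treat set of all randomized women as primary.

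The cost is SAP wording, one more covariate and one more supportive analysis. The data are already collected, no woman leaves the primary analysis, and recruitment is unaffected. The term-birth analysis will be smaller and should be read as a check on consistency. The change does not restore the power of the unadjusted log-rank or proportion tests, and it does not address illness in term infants.

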#### *OUTCOME ASSESSMENTS*

- A questionnaire about breastfeeding (including psychosocial factors related to breastfeeding and introduction of alternatives to breastmilk) and contraceptive use will be administered at each contact. Timing of lactogenesis II will be assessed at Week 2 unless it occurred prior to discharge. Timing of postpartum sexual activity initiation will also be assessed. At any point when the subject reports cessation of breastfeeding, a questionnaire will be administered to assess reasons for discontinuation.

- The Edinburgh Postnatal Depression Scale (EPDS) will be administered at each contact as a screening tool for postpartum depression.(5) If a subject scores  $\geq 12$  on the EDPS, she will be referred to the Magee Behavioral Health clinic or to a behavioral health clinic of her choice and her primary obstetrician or midwife will be notified.
- Subjects will be asked if they had any visits with their primary obstetrician, midwife, or any other provider since the last contact. Records will be requested from all reported visits.
- The next telephone contact will be scheduled (when applicable).

**5.8 Data analysis:** Analysis will be performed using Stata 10 (StataCorp LP, College Station, TX).

- 1) The primary analyses will use intention-to-treat data. The intention-to-treat group will be defined as all randomized subjects. Infants who are fed pumped breastmilk will be considered as breastfeeding. Exclusive breastfeeding will be defined as breastfeeding without introduction of alternatives to breastmilk. A secondary analysis looking only at women who received at least one injection of DMPA will also be performed.
- 2) Survival analysis will be used for all time series data, including time to discontinuation of breastfeeding and time to introduction of alternatives to breastmilk. Data will be censored at the last date of contact. Breastfeeding will be the outcome variable. The log-rank test will be used for unadjusted comparison of the groups and presented graphically using a Kaplan-Meier curve. Cox proportional hazards model will be used to control for age, race, education, marital status, and prior breastfeeding experience while examining the association between timing of DMPA administration and discontinuation of breastfeeding.
- 3) Normally distributed continuous variables will be compared using Student's t-tests. The Mann-Whitney rank-sum test will be used to compare other continuous variables. Proportions will be compared using chi-square tests or Fisher's exact tests as appropriate.

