## ABSTRACT

In the United States, depot medroxyprogesterone acetate (DMPA) is frequently administered prior to hospital discharge with the belief that women who delay initiation of DMPA may face higher risk of unintended pregnancy and that administration postpartum has little to no negative effect on breastfeeding. Administering DMPA to breastfeeding women has not been widely questioned because the limited existing studies do not show any adverse impact of DMPA on breastfeeding. However, these studies used inappropriate control groups and did not control for prior lactation experience.(1-3) We recently conducted a randomized controlled trial (RCT) which found that significantly fewer women who underwent immediate postplacental levonorgestrel-releasing IUD (LNG-IUD) placement continued to breastfeed at 6 months compared to those who underwent insertion at 6-8 weeks postpartum.(4) Since systemic levels of progestins are much less with the LNG-IUD compared to DMPA, we became concerned about potential effects of administering DMPA immediately postpartum.

We therefore propose to enroll 184 women who plan to breastfeed and use DMPA postpartum in a RCT to investigate whether the timing of postpartum administration of DMPA (prior to hospital discharge vs. 4-6 weeks postpartum) affects the duration or exclusivity of breastfeeding among women who plan to breastfeed their infants. Secondary outcomes will include rates of use of highly effective contraception (defined as DMPA, IUD, implant, sterilization, or lactational amenorrhea) and postpartum depression. Outcomes will be assessed by phone at 2, 4, 6, 8, 12, 16, 20, 24, and 28 weeks postpartum.

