### HYPOTHESES:

1. Women who receive DMPA 4-6 weeks after delivery will be more likely than women who receive DMPA prior to hospital discharge to exclusively breastfeed for 6 months.
2. Women who receive DMPA 4-6 weeks after delivery will be as likely as women who receive DMPA prior to hospital discharge to use highly effective contraception (i.e. DMPA, intrauterine device (IUD), implant, sterilization, or lactational amenorrhea) at 6 months after delivery.
3. Women who receive DMPA 4-6 weeks after delivery will be no more likely than women who receive DMPA prior to hospital discharge to develop postpartum depression as measured by the Edinburgh Postnatal Depression Scale.(5)

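### Depression is first scored at week 2, after randomization and after the Group 1 injection, and the depression history collected at enrollment enters no depression comparison: a minor, cheaply improved weakness in a secondary outcome

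*Combined protocol and SAP*

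**What the plan says.** Hypothesis 3 (section 1) compares the two timings on how likely women are "to develop postpartum depression as measured by the Edinburgh Postnatal Depression Scale". The Abstract lists depression as a secondary outcome.

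The instrument appears once in the schedule, in the outcome assessments of 5.7: "The Edinburgh Postnatal Depression Scale (EPDS) will be administered at each contact as a screening tool for postpartum depression". Section 5.7 opens with "Subjects will be contacted by phone at the following time points", and the first window is week 2, day 12-19. The Abstract agrees: "Outcomes will be assessed by phone at 2, 4, 6, 8, 12, 16, 20, 24, and 28 weeks postpartum".

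For Group 1, section 5.6 says "An investigator will order DMPA to be administered prior to hospital discharge". Group 2 is due its injection 4-6 weeks after delivery.

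Before randomization, 5.4 collects psychiatric history, including depression and anxiety, and 5.2 excludes "History of severe clinical depression". No EPDS is listed at enrollment, at the in-hospital eligibility interview or in the pre-discharge questionnaire.

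In 5.8 the only adjusted model is the Cox model for breastfeeding discontinuation, which has no depression covariate. Other proportions get chi-square or Fisher tests, and continuous variables get t-tests or rank-sum tests. A score of 12 or more appears only as a trigger for referral.

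**The concern.** A hypothesis about onset needs some way to tell new depression from depression already present. Here the exclusion covers severe history only, so women with milder or current symptoms can be randomized, and their first score comes after allocation. The week 2 score cannot stand in as a baseline: it follows the injection in Group 1, and it is post-randomization in both arms.

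Two things are at stake. If women above threshold at randomization are counted as cases, the same number is added on average to both arms and the ratio between arms moves toward 1. And in arms of this size, a chance difference in current symptoms at randomization would go unnoticed and could not be adjusted for. The plan has a reason to care: section 2 cites an increased depression risk after another early postpartum injectable progestin and says the timing of DMPA has not been studied for this outcome.

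**Working it through.** **The plan's own figure.** Section 5.9 gives 70 per group for breastfeeding continuation of 0.35 versus 0.60. Exact two-sided Fisher power is 0.8095 at 70 per group and 0.7992 at 69, so 70 reproduces. Inflation gives 140 / (0.90 × 0.85) = 183.01, rounded up to 184. This figure concerns breastfeeding; there is no sample size, power or margin for depression.

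**Order of events.** Eligibility interview, randomization and Group 1 injection (all before discharge), then first EPDS (day 12-19), then Group 2 injection (4-6 weeks). No reading of the schedule puts a score before allocation.

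**How many cases to expect.** 184 × 0.90 = 165.6 randomized, about 82 per arm. At the 10-15% rate quoted in section 2, that is about 8-12 women per arm.

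**Effect of counting cases already present.** Let q be the proportion above threshold at randomization, equal in both arms, and i the new-onset rate among the rest. The observed rate is q + (1 − q) × i. The documents give no q and no arm-specific i. I assume i = 10% in Group 2 and 20% in Group 1, q from 0 to 15%, and 70 per arm. For q = 5%: 0.05 + 0.95 × 0.10 = 0.145 and 0.05 + 0.95 × 0.20 = 0.240.

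Power uses the two-sided 5% normal approximation without continuity correction: Φ{[|p1 − p2| − 1.96 √(2p̄(1 − p̄)/n)] / √[(p1(1 − p1) + p2(1 − p2))/n]}. Fisher's test would give somewhat less. The last column sets aside women above threshold, so n = 70(1 − q) and the ratio stays at 2.00.

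| q | Group 2 | Group 1 | Ratio | Difference (points) | Power, all counted | Power, prevalent cases set aside |
|---|---|---|---|---|---|---|
| 0 | 0.100 | 0.200 | 2.00 | 10.0 | 38% | 38% |
| 5% | 0.145 | 0.240 | 1.66 | 9.5 | 30% | 36% |
| 10% | 0.190 | 0.280 | 1.47 | 9.0 | 24% | 35% |
| 15% | 0.235 | 0.320 | 1.36 | 8.5 | 20% | 33% |

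With assumed rates of 15% and 30% the pattern is the same: the ratio falls from 2.00 to 1.74, 1.57 and 1.46, and power from 0.567 to 0.481, 0.412 and 0.355. Swapping the arms changes none of these figures.

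**Chance imbalance in q.** The 95% range for the difference between arms of 70 is ±1.96 √(2q(1 − q)/70), which is ±7.2, ±9.9 and ±11.8 points for q = 5%, 10% and 15%.

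**The case against.** The case for leaving the plan alone is substantial, and most of it stands.

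- **No systematic bias.** Randomization takes place after delivery and after eligibility is rechecked, so earlier depression is balanced in expectation. Chance imbalance is already allowed for in the 5% error rate of an unadjusted randomized test. What remains is lost precision and the inability to see imbalance in current symptoms; history gives only a coarse view.
- **Counting of prevalent cases is inferred.** A reader might conclude that a woman above threshold at randomization will be recorded as having developed depression. The documents do not say so: 12 or more is a referral trigger, no depression endpoint is defined, and her score might have fallen by week 2. The table therefore shows what happens if every such woman is counted.
- **Direction.** A reader might infer that dilution favours the sponsor's hypothesis. Hypothesis 3 is one-directional: it says delayed women are not at higher risk. The only prior signal cited would raise Group 1, and in that case the hypothesis is true anyway. Dilution can mask a difference either way, but it wrongly supports Hypothesis 3 only if delayed DMPA raises depression.
- **Scale.** The absolute difference barely moves, and the plan names no relative measure.
- **Precision gain.** Baseline adjustment can cut the variance of a continuous score by the squared baseline-to-follow-up correlation. The documents give no such correlation, and the gain cannot be carried over to a yes/no outcome.
- **Power is low regardless.** On the assumed rates it is 33-36% even with prevalent cases set aside.

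None of this removes the point that relevant history is collected and left unused, or that a form already in the study could be given at an interview already held.

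**Conclusion.** The point holds as a minor improvement to a secondary outcome. The plan states a hypothesis about onset, takes its first score after allocation and after one arm is treated, and uses no baseline information on depression in the comparison.

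The consequence is imprecision and possible attenuation. On the first set of assumed rates, 5-15% prevalence at randomization costs 8 to 18 percentage points of power (38% to 30-20%) and takes the ratio from 2.00 to 1.66-1.36, while the risk difference loses 0.5 to 1.5 points. These sizes rest on assumed prevalence, assumed new-onset rates and the assumption that prevalent cases are counted. The documents do not support calling the comparison biased, or saying that the design is tilted toward Hypothesis 3.

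**What to change.** 1. **Analysis wording, all randomized women.** In 5.8, add a depression comparison adjusted for the depression and anxiety history from 5.4 c, alongside the unadjusted test: for example, logistic regression for EPDS of 12 or more and linear regression for EPDS score, at a contact or contacts named in advance. With about 8-12 expected cases per arm, keep to one or two history terms. This needs no new data and covers women already randomized.

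2. **Baseline score, women not yet randomized.** Add the EPDS to the in-hospital interview in 5.6, before the packet is opened, and use it as a covariate. Report first EPDS of 12 or more among women below 12 at that interview as a supporting analysis limited to those women. That group is defined before allocation, so the comparison remains randomized. The all-randomized comparison stays the main one.

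**Cost.** The first change is wording only. The second takes a few minutes per woman for a 10-item form already in use. The handling of a positive score at that interview would have to be reconciled with 5.7. Section 5.11 shows enrollment well under way (62 women in the 13 months after postpartum enrollment was allowed), so women already randomized will have no baseline score and cannot enter the supporting analysis.
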